Variability and Specificity in Reactive Stabilization Movements to Diverse Slip Perturbations

NCT03755336

04-20-2021

Study Protocol

For all gait collections, participants will arrive at the Biomechanics Research Building on the University of Nebraska at Omaha campus. All participants will be consented and screened prior to gait testing. During the consent process, participants will be asked if they can be contacted again for future research studies. During the screening, participants will undergo a short medical history and a physical activity questionnaire. Participants will be asked to report their previous falls before the intervention. Participants will also be asked to be contacted through a phone call 6-months post intervention to record their fall history within the 6 months period.

Participants will be asked to put on a form fitting suit for data collection. Body weight, height and extremity anthropometry will be collected (length of arm and leg segments). Retroreflective markers will be placed on the legs, arms, torso and head to obtain whole- body kinematic data. A ceiling-mounted safety harness will also be fitted to each participant. Prior to performing any walking trials, the participants will be allowed to "sit" in the harness to experience how it feels when it catches them.

On the initial visit, participants will perform informed consent, then be asked to provide demographic information (age, gender), height and body mass measurements, and a medical questionnaire to assess exclusion criteria. Questionnaires to assess for physical activity, and previous falls will be administered. Upper and lower body strength will be measured using a hand held dynamometer during the first and last visits. On each of the three visits, participants will perform a gait variability assessment followed by a diverse slip perturbation assessment.

Functional design and validation of a wearable apparatus for administering lifelike slip perturbations: To investigate slips under diverse slipping conditions, a Wearable Apparatus for Slipping Perturbations (WASP) has been developed and validated by students working in the Biomechanics Research Building under supervision of the PI. Currently, the WASP can be worn over standard athletic shoes and triggered remotely by the experimenter. Before the WASP is triggered, the participant walks with a high friction interface between the rubber external sole and laboratory floor. When the experimenter wirelessly triggers the WASP, the external sole releases from the participant's shoe, transitioning available friction to a low friction interface between two layers of PTFE film within 10 milliseconds. Friction is reduced from a dynamic coefficient of approximately $m=0.55$ (athletic shoes on a basketball court) to $m=0.10$ (akin to shoes on ice).

Gait variability assessment procedures: Before recording data, retroreflective markers will be placed on specific anatomical locations. These locations are defined to create a full- body dynamics model. Following familiarization, subjects will walk on a treadmill for 5 minutes at a prescribed pace of 1.3 meters per second while whole body kinematics are collected with a 17-camera motion capture system. Both linear and nonlinear measures of gait variability will be calculated to determine possible relationships between these measures and other outcome variables such as learning rate for reactive movements and fall rate.

Diverse slip perturbation assessment procedures: subjects will be outfitted with WASP and a safety harness connected to an overhead rail system and walk overground back and forth across a large motion capture area. Previous studies show that walking speed is highly correlated with some

outcome measures, specifically variations in whole body angular momentum, gait variability measures, and loss of balance following a slip.

Therefore, investigators will control gait speed across all subjects to 1.3 m/s, a typically comfortable speed for older adults. Participants will be informed that a slip may occur, and that if slipped, they should attempt to maintain balance and continue walking. Participants will then be slipped without warning at a randomly chosen time after 1 to 3 minutes of walking. Slips will be administered to both feet simultaneously during early, middle or late stance in a randomized order. After each slip, participants will rest seated for 5 minutes. During this rest period, motion capture data and force data from the harness will be downloaded, and the WASP will be outfitted on the participant for the next trial. Participants will complete four slips in each of early, middle, and late stance on each visit. Measures of falls, slip severity, and reactive stabilization movements will be calculated. Since falls will be prevented from a harness system in this study, a trial will be classified as a fall if the load cell in the harness system measures a peak force in excess of 30% of the participant's body weight.

Statistical Analysis Plan

For each outcome variable (e.g., slip severity, reactive stabilization movements, fall rates), normality assumptions will be assessed using Shapiro-Wilk tests and visual inspection of histograms and Q-Q plots. Descriptive statistics (means \pm SD or medians with interquartile ranges) will be reported based on these assessments.

To determine differences between age groups (younger vs. older adults) on continuous outcomes (e.g., slip severity measures, reactive stabilization kinematics), linear mixed- effects models will be employed, with participant included as a random factor to account for repeated measurements within individuals. Post-hoc comparisons, when necessary, will be adjusted using Tukey or Holm-Bonferroni corrections.

For binary outcomes (fall/no fall, defined by harness load exceeding 30% of body weight), generalized linear mixed-effects models (logistic regression) will be used, again with participant included as a random effect and age group as the primary fixed factor.

All statistical analyses will be performed using R statistical software, with significance determined at $\alpha = 0.05$. Any data transformations or handling of missing data will be clearly documented and justified.

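### Should the SAP adjust the age comparison for the walking speed achieved in the overground slip trials?

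*Combined protocol and SAP*

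**What the plan says.** Under the diverse slip perturbation procedures, the Study Protocol gives its reason for caring about speed: earlier work ties it closely to certain "outcome measures, specifically variations in whole body angular momentum, gait variability measures, and loss of balance following a slip". The consequence it draws is a design measure: "Therefore, investigators will control gait speed across all subjects to 1.3 m/s, a typically comfortable speed for older adults".

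The two assessments differ in how speed is set. For gait variability, "subjects will walk on a treadmill for 5 minutes at a prescribed pace of 1.3 meters per second". For the slips, participants "walk overground back and forth across a large motion capture area". The protocol states no pacing method, tolerance or rule for off-speed trials. After each slip, "motion capture data and force data from the harness will be downloaded". On volume, "Participants will complete four slips in each of early, middle, and late stance on each visit". A fall is defined from the harness, with the threshold expressed as a percentage of body weight: "a trial will be classified as a fall if the load cell in the harness system measures a peak force in excess of 30".

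The Statistical Analysis Plan compares younger with older adults by linear mixed models (continuous outcomes) and logistic mixed models (falls). The only terms it names are age group and a participant random effect. Speed is not mentioned.

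**The concern.** The protocol itself names speed as a strong correlate of loss of balance and wants everyone at the same speed. On the treadmill that is guaranteed. Overground, 1.3 m/s is a target that people can miss, and younger and older adults might miss it differently. A participant random effect handles correlation within a person but does not remove a speed difference between groups. If such a difference arose, part of the age contrast for falls, and for any speed-related kinematics, would reflect speed, and a reader could not tell how much. Motion capture is already being recorded, so a speed table and a speed-adjusted sensitivity analysis look like cheap protection for the equal-speed intention.

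**Working it through.** **Which outcomes are exposed.** The protocol names three speed-related outcomes.

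- Gait variability is assessed on the treadmill, where the belt fixes speed.
- Angular momentum is not named in the SAP. It matters only if it is analysed among the reactive stabilization kinematics.
- Loss of balance enters through harness-defined falls, which is an inference.

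Slip severity, which the SAP does name, is not on the protocol's list.

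**Inputs.** From the documents: target 1.3 m/s, and 4 slips x 3 stance phases x 3 visits = 36 slips per person. There is no planned figure to reproduce: the documents give no sample size, speed SD, slope or group gap. Everything else here is assumed: 20 per group; speed SD 0.04 m/s between and 0.05 m/s within persons; residual SD 1; participant SD T of 0.5 or 1.0; speed slope b of 0.5 or 1.0 residual SD per 0.1 m/s, equal within and between persons; no age effect at equal speed; two-sided 5% test.

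**Shift of the unadjusted contrast** = b x gap / 0.1.

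**Its standard error** = sqrt{(2/20) x [T² + (0.4b)² + (1 + (0.5b)²)/36]}.

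- b = 1.0, T = 0.5: sqrt{0.1 x (0.25 + 0.16 + 0.0347)} = 0.211.
- b = 0.5, T = 1.0: sqrt{0.1 x (1 + 0.04 + 0.0295)} = 0.327.

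| Gap (m/s) | Shift, b = 0.5 | Shift, b = 1.0 | Rejection, b = 0.5, T = 1.0 | Rejection, b = 1.0, T = 0.5 |
|---|---|---|---|---|
| 0 | 0 | 0 | 5% | 5% |
| 0.02 | 0.10 | 0.20 | 6% | 16% |
| 0.05 | 0.25 | 0.50 | 12% | 66% |

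Rejections use the normal approximation; mixed-model simulation on the same inputs gave 6-15% at 0.02 and 11-64% at 0.05. They are false positives only if the target is the contrast at equal speed. For the contrast as walked they are correct. The 0.05 m/s row assumes a gap of 0.05/0.04 = 1.25 between-person SDs despite active speed control. For falls, an assumed 0.7 log-odds per 0.1 m/s gives 0.7 x 0.2 = 0.14 at 0.02 m/s and 0.7 x 0.5 = 0.35 at 0.05 m/s (odds ratio about 0.70).

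**What adjustment does if speed is only a marker.** The natural adjustment enters participant mean speed and the trial's deviation from it. The age contrast is then corrected with the between-person slope. Suppose speed has no effect, there is no age effect, and the participant component of the outcome (SD 0.5) is a trait correlated 0.6 with personal speed.

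- Spurious slope = 0.6 x 0.5 / 0.04 = 7.5 SD per m/s.
- Reliability of a 36-trial mean = 0.04² / (0.04² + 0.05²/36) = 0.0016 / 0.00167 = 0.958.
- Fitted slope = 7.5 x 0.958 = 7.19 SD per m/s.
- Bias created = 7.19 x 0.02 = 0.14 SD and 7.19 x 0.05 = 0.36 SD.

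Simulation of this case gave 0.14 to 0.15 and 0.35 SD, with the unadjusted contrast at about zero. This is the same order as the shift that adjustment is meant to remove.

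**Precision cost.** If speed explains no between-person variance, the standard error is multiplied by 1/sqrt(1 - R²), with R² = (0.05²/4) / (0.05²/4 + 0.00167) = 0.272 at a 0.05 m/s gap. That gives 1.17.

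**What a speed table could show.** SE of the group gap = sqrt(2/20) x sqrt(0.04² + 0.05²/36) = 0.316 x 0.0409 = 0.0129 m/s. The 95% half-width is 2.02 x 0.0129 = 0.026 m/s. A table would flag a large failure of control but could not exclude a gap of 0.02 m/s.

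**The case for a change.** The best case for a change is that control is only an intention: the protocol does not say how overground speed is held, and nothing in the SAP would show whether 1.3 m/s was met. Speed just before release is not part of the slip response, so it is a legitimate covariate. The planned contrast could remain the main analysis, with the adjusted one beside it. If the speed slope is causal, the two-term adjustment works: in simulation it brought the linear shift to at most 0.04 SD and rejection to 4-7%.

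Part of this stands. The SAP has no summary of achieved speed, and one by age group and visit would help readers where motion capture permits. The documents do not, however, confirm that a full straight stride before each release is recorded. The case for a prespecified adjusted contrast is weaker. Its good performance depends on simulating a slope free of confounding by personal traits, and the data cannot establish that. Age may also act through speed, in which case adjustment removes part of the effect under study. Such an analysis would be exploratory, conditional on observed speed, and should not be called the comparison at equal speed.

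**Conclusion.** No change to the plan is needed. The protocol meets the speed concern by controlling speed, at a value chosen as comfortable for older adults, which makes a slower older group less likely. Harm needs control to fail, to fail differently by age, and the between-person slope to be non-zero; the documents show none of these. If the plan is followed as written, the age contrast is sound; if speeds drift apart, it is still the age difference as walked.

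The possible shift runs from zero to 0.50 residual SD across gaps of 0 to 0.05 m/s, but every input behind that range except the 36 slips is assumed. Adjustment can introduce an error of similar size, so it is a debatable trade-off and not a correction. The missing speed summary is a reporting detail that analysts can supply from their own recordings.

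### Neither SAP model names stance phase, the slip condition the protocol varies in randomised order, so phase and age × phase have no prespecified test

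*Combined protocol and SAP*

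**What the plan says.** The design of the slip trials is in the Study Protocol, under the diverse slip perturbation assessment procedures. Phase is assigned by the experimenter: "Slips will be administered to both feet simultaneously during early, middle or late stance in a randomized order". It is also replicated: "Participants will complete four slips in each of early, middle, and late stance on each visit". The opening part of the Study Protocol sets the number of sessions: "On each of the three visits, participants will perform a gait variability assessment followed by a diverse slip perturbation assessment".

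The Statistical Analysis Plan gives the linear mixed model the purpose of comparing younger with older adults, "with participant included as a random factor to account for repeated measurements within individuals". The logistic model for falls is described as "again with participant included as a random effect and age group as the primary fixed factor". One further sentence may bear on the point: "Post-hoc comparisons, when necessary, will be adjusted using Tukey or Holm-Bonferroni corrections". It does not say which factor or which contrasts are meant. Stance phase, slip type and interaction terms appear nowhere in the SAP.

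The documents state no formal hypothesis about phase. The study's interest in it is visible in the title, "Variability and Specificity in Reactive Stabilization Movements to Diverse Slip Perturbations", and in the reason given for building the slip device: "To investigate slips under diverse slipping conditions".

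**The concern.** Phase is the only slip condition that the protocol describes varying by design, and it is balanced within each participant. A study whose title concerns specificity to diverse slips would be expected to say how that condition enters the analysis. Under the SAP as written, an age-only model and an age × phase model are both compliant, yet they answer different questions.

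Four things are at stake:

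- An age-only model cannot show whether older adults react differently to one kind of slip than to another.
- If the analyst adds phase later, the choice of terms and contrasts will have been made with the data in hand.
- In the logistic model, leaving out a strong phase effect moves the estimated age odds ratio toward 1 relative to the within-phase odds ratio.
- If phase terms are added but the participant effect is kept as a random intercept only, the age × phase test rejects too often.

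**Working it through.** **Inputs from the documents.** There are three phases, four slips per phase per visit and three visits, so 4 × 3 = 12 slips per phase and 36 per participant. Alpha is 0.05; sidedness is not stated, and two-sided is assumed here. The plan gives no sample size, SD, effect size or fall rate, so it has no figure to reproduce.

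**Assumed inputs.** n = 20 per group (10 and 30 as a range); between-person SD 1; residual SD 1; person-by-phase SD τ from 0.2 to 1.0; age effects in units of the residual SD. Slips within a phase are treated as exchangeable over visits.

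**1. Averaged age test.** An effect of 0.5 in one phase only averages to 0.5/3 = 0.167. An effect of +d, 0, −d averages to 0. The test is a t-test on participant means, with SE = √[(2/n)(1 + τ²/3 + 1/36)]. At τ = 0.5 this is √(0.1 × 1.111) = 0.333, so the noncentrality is 0.167/0.333 = 0.50. On 38 df the power is about 8%; over the range of τ it is 7-8%.

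**2. Age × phase test (2 df).** The noncentrality is λ = (n/2) Σ(δⱼ − δ̄)² / (τ² + 1/12). For the one-phase effect, Σ = 0.5² × 2/3 = 0.167. At τ = 0.5, λ = 10 × 0.167/0.333 = 5.0. Power from the noncentral F with 2 and 2n − 3 = 37 df is 47%.

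| Age effect by phase (20 per group) | Averaged test | Age × phase, by τ |
|---|---|---|
| 0.5 / 0 / 0 | 7-8% | 90% (0.2), 76% (0.3), 47% (0.5), 29% (0.7), 17% (1.0) |
| 0.5 / 0.25 / 0 | 10-12% | 79% (0.2), 63% (0.3), 37% (0.5), 14% (1.0) |
| 0.5 / 0.5 / 0.5 | 26-33% | 5% at every τ |

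For the one-phase effect at τ = 0.5, age × phase power is 24% with 10 per group and 66% with 30. The mixed-model form of the F test, with 2 and 2(2n − 2) df, gives 91%, 78%, 49%, 30% and 18% for the first row.

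**3. Locating the effect.** The age contrast in the affected phase has SE = √[(2/n)(1 + τ² + 1/12)]. At τ = 0.5 this is √(0.1 × 1.333) = 0.365, so the noncentrality is 0.5/0.365 = 1.37. At alpha/3 the power is 14%, and 9-17% over the range of τ. Three unadjusted tests at 0.05, if independent, would carry a familywise error of 1 − 0.95³ = 0.143.

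**4. Logistic model.** Take a within-phase age odds ratio of 2.0 and a middle-phase fall rate of 30% in younger adults, ignoring the participant effect.

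- Phases 1 logit apart: younger 13.6/30.0/53.8%, mean 32.5%; older 24.0/46.2/70.0%, mean 46.7%. The pooled odds ratio is (0.467/0.533)/(0.325/0.675) = 1.82.
- Phases 2 logits apart: means 37.2% and 47.6%, pooled odds ratio 1.54.

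The large-sample limit of the age-only random-intercept model (random-intercept SD 0.5-1.0, 36 slips per person) agrees, at about 1.8 and 1.55.

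**5. Type I error of age × phase with a random intercept only.** Under the null, the interaction mean square has expectation 12τ² + 1. The model tests it against a residual that pools the person-by-phase mean square (76 df, same expectation) with the within-cell error (40 × 3 × 11 = 1,320 df, expectation 1). At τ = 0.5 the pooled residual is (76 × 4 + 1,320)/1,396 = 1.163, against a numerator expectation of 4. With the 5% critical value of 3.00, the rejection rate is about exp(−3.00 × 1.163/4) = 0.42. At τ = 0.2, 0.3 and 1.0 it is about 12-13%, 22% and 68%.

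For the logistic model, simulation (2,181 to 2,805 trials per setting, 20 per group, likelihood-ratio test) gave 8%, 13% and 36% at logit SDs of 0.3, 0.5 and 1.0. With a participant-by-phase random effect the rates were 5.5%, 5.5% and 5.7%.

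**The case against.** The strongest reply is that the SAP's stated purpose is an age comparison, and an age contrast averaged over varied slips is a coherent target. Randomising phase may serve simply to make slips unpredictable. The SAP does not claim that its terms are exhaustive: calling age group the primary factor implies others, and a Tukey adjustment is pointless for a two-level factor, so a factor with more levels was probably in mind. A participant random factor need not mean an intercept only. The logistic attenuation is non-collapsibility, a difference between two estimands, rather than confounding.

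Much of this stands. No phase hypothesis is stated, the averaged linear contrast is sound with complete data, and the type I figures apply only if phase is added with an intercept-only structure. The power figures depend on an unknown person-by-phase SD, and the phase-specific follow-up contrasts are weak at 20 per group.

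It does not answer the main point. A hint that some multi-level factor might be included is not a prespecified test: the factor could be phase, visit or slip number. The averaged contrast, however coherent, says nothing about specificity across slip conditions.

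**Conclusion.** The concern holds: neither model specifies phase or age × phase, and nothing else in the SAP supplies the test. This is an incomplete specification that should be fixed, not a bias in the planned age comparison.

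Confidence is high for the omission and lower for the size of its consequence, because every SD, effect size, sample size and fall rate used above is assumed. On those assumptions, the averaged test is nearly blind to an age effect confined to one phase. The age × phase test is much stronger when individuals vary little in their response to phase, and only modestly better when they vary a lot. When the age effect is the same in all phases the ordering reverses, so neither test replaces the other. The random-effects structure also has to be stated: an intercept-only model would make a later age × phase result unreliable if people differ in their phase response.

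Visit and slip order are also absent from both models; that is a separate matter, not assessed here.

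**What to change.** In both the linear and the logistic mixed models:

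- List the fixed effects as age group, stance phase (early, middle, late) and age group × stance phase.
- List the random effects as participant and participant-by-phase.
- Test age × phase on 2 df, then report the age contrast with its confidence interval within each phase, Holm-adjusted over the three. Name these as the post-hoc comparisons the SAP refers to.
- Keep the age contrast averaged over phases, and say which of the two tests leads.
- Prespecify that if the logistic model does not converge, the participant-by-phase effect is dropped and the age × phase result for falls is labelled exploratory.

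The cost is SAP wording, four extra fixed-effect parameters (two for phase, two for the interaction) and one extra variance in each model. The models become slightly more complex and the logistic fit may fail to converge. Phase is set for every slip, so no further data are needed and no trial procedure changes. At around 20 per group the phase-specific contrasts should be read mainly through their confidence intervals, because their power is low.

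### Does testing the normality of each outcome, fall rates included, leave the mixed-model age comparison unsound?

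*Combined protocol and SAP*

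**What the plan says.** The first paragraph of the Statistical Analysis Plan covers every outcome and names fall rates among the examples: "For each outcome variable (e.g., slip severity, reactive stabilization movements, fall rates), normality assumptions will be assessed using Shapiro-Wilk tests", with histograms and Q-Q plots alongside. The consequence follows at once. Means with SDs, or "medians with interquartile ranges) will be reported based on these assessments". The paragraph gives the check no other role.

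The models come in separate paragraphs. Continuous outcomes go to a linear mixed model, "with participant included as a random factor to account for repeated measurements within individuals". Falls have their own rule: "For binary outcomes (fall/no fall, defined by harness load exceeding 30% of body weight), generalized linear mixed-effects models (logistic regression) will be used". Neither paragraph mentions residuals, the distribution of the random effects, or model fit. The last paragraph adds "Any data transformations or handling of missing data will be clearly documented and justified".

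On the amount of data, the protocol's slip assessment section says "Participants will complete four slips in each of early, middle, and late stance on each visit", and the Study Protocol section sets three visits. The gait variability section counts fall rate among "other outcome variables such as learning rate for reactive movements and fall rate".

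**The concern.** A linear mixed model does not require a normal outcome. It assumes normal residuals and normal random effects. The SAP tests the outcome and does not say whether the values tested are single slips or participant means.

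- **Pooled slips** are clustered within people and shifted by age group and stance phase. They can fail a normality test when the model is exactly right.
- **Participant means** average the slip-level residuals away, so they cannot show whether those residuals are normal.

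If analysts transformed outcomes on the strength of such a test, or took a pass as proof that the model fits, the age comparison could be misreported.

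Falls add a second worry. Normality has no meaning for a fall/no-fall result on one slip, yet fall rates sit under the same rule, and the only descriptive summaries offered are mean with SD or median with interquartile range. For 0/1 data, a median with quartiles can hide a real difference between groups.

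**Working it through.** **Inputs.** From the documents: 4 slips × 3 stance phases = 12 per visit, and 12 × 3 visits = 36 per person; α = 0.05. The documents give no sample size, variance or fall rate, so there is no planned figure to reproduce. Assumed: 10 to 20 people per group, residual SD σ = 1, between-person SD τ = 0.5 to 1.5, age difference 0 to 1 residual SD.

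**1. How the test behaves when the model is exactly true.** Shapiro-Wilk at 5% rejects in these shares of simulated datasets:

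| Values tested | Rejections |
|---|---|
| Pooled slips | 6–79% |
| Pooled slips, one age group | 5–70% |
| Participant means | 4–6% |
| Conditional residuals | 4–6% |

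Pooled slips are therefore a poor check of the model. The width of the first range reflects the assumed grid.

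**2. What participant means can show.** With a random intercept and equal slips per person, participant i's mean is the group mean plus bᵢ plus the average of 36 residuals, with variance τ² + σ²/36. The predicted random effect is the group-centred mean multiplied by τ²/(τ² + σ²/36):

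- τ = 0.5: 0.25/(0.25 + 0.0278) = 0.90
- τ = 1.5: 2.25/(2.25 + 0.0278) = 0.99

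Apart from centring by group, a check on participant means is therefore close to a check on the random effects. With exponential random effects (skewness 2) and no age difference, Shapiro-Wilk on participant means rejects in 56–99% of datasets.

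It does not see the residuals. With t residuals on 5 df, or residuals of skewness 1, it rejects in 4–8%, against 99.7–100% on conditional residuals.

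**3. Does that blindness matter for the age test?** Averaging 36 residuals divides their skewness by √36 = 6, from 1 to about 0.17. It divides the excess kurtosis of the t distribution on 5 df by 36, from 6 to about 0.17. With balanced data the mixed-model age test is equivalent to a t-test on participant means. Its type I error at nominal 5%, over 3000 runs per setting (Monte Carlo standard error about 0.4 points):

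| Violation | Type I error |
|---|---|
| t residuals, 5 df | 4.7–5.3% |
| Residuals with skewness 1 | 3.6–6.0% |
| Exponential random effects | 3.7–5.3% |

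A repeat of these settings with fresh random numbers stayed within 3.6–6.0% for every violation.

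**4. Falls.** The upper quartile of a 0/1 variable is 0 whenever its proportion is below 25%. Falls on 10% and on 24% of slips, an odds ratio of (0.24/0.76)/(0.10/0.90) = 2.8, would both read 0 (0–0). That needs slips as the unit, and a single slip has no rate. As per-participant rates (logit SD 0.8), the same values read 8% (3–14%) and 22% (11–33%). At logit SD 1.2 they read 6% (3–14%) and 19% (8–36%). If the mean is reported instead, the average of fᵢ/36 over n people is Σfᵢ/(36n), which is the overall proportion of slips that ended in a fall.

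**The case for a change.** The strongest case for a change is that the sentence names what is tested, and it is not residuals. A plan that goes as far as naming Shapiro-Wilk, histograms and Q-Q plots can hardly be read as silently specifying model diagnostics too. The SAP leaves transformations open without saying what evidence would support one, and a rejection on pooled slips would be bad evidence. The remedy costs a few sentences and some plots from models that will be fitted anyway.

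Most of this stands as description. No model diagnostic is named, the unit of the check is not given, and no count or percentage of falls is planned. It falls short on consequence. Nothing in the SAP triggers a transformation or a change of model from the test, and any transformation must be justified openly. The high rejection rates for pooled slips measure the test in a job the SAP does not give it. They are also rejection rates of a normality test; none is a bias, coverage or type I error of the planned age comparison. Where type I error was examined, it stayed near nominal.

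Two limits remain. The simulations cover the age comparison in balanced data. Comparisons within people (stance phase, visit), unequal variances and dropout were not examined.

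**Conclusion.** No change to the plan is needed. The check on outcome distributions suits its one stated purpose, the choice of descriptive summary. The linear and logistic mixed models still give a sound age comparison if the SAP is followed as written: type I error was 3.6 to 6.0% in the settings tried. The 0 (0–0) display arises only if slips are the unit of a fall rate, which is not how the term naturally reads; per-participant rates stay informative.

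What remains is missing detail of a kind that analysts supply as routine. They would look at residual and random-effect plots before transforming anything, and would give the percentage of falls beside the logistic model. Writing this down would be harmless, but it changes no result shown here.

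The conclusion rests on assumed group sizes of 10 to 20, between-person SD of 0.5 to 1.5 times the residual SD, 36 slips completed per person, and reading the SAP to mean that no modelling decision hangs on the Shapiro-Wilk result.
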